6.7 Missing Data for Efficacy and Safety Endpoints

Missing data for each efficacy endpoint will be handled as described in Sections 9.1 and 9.3.4.

For continuous endpoints, change from baseline will be set to missing at visits with missing postbaseline values or where data were imputed to missing. Continuous efficacy endpoints will be set to missing for subjects who received any of the following not allowed medication post-baseline procedure:

- Corticosteroids (e.g., oral, parenteral or injection, budesonide or other sinus steroid irrigations/rinses or drops, breath powered Xhance, nebulized steroids administered nasally or other drug eluting stents) through Day 45; or
- Biologics for CRS treatment (e.g., Dupixent).

For binary endpoints, subjects with missing efficacy data, early withdrawals, and/or subjects who received not allowed corticosteroids or biologics for chronic sinusitis condition attributable to the FSO/frontal recess will be imputed as a treatment failure. If a subject initiates high-dose steroid for other reasons not involving FSO/frontal recess, this does not represent treatment failure.

Additional rules for handling of missing data and rescue treatments are detailed below:

- *Missing efficacy data.* Visits with missing data (due to a missed visit or missing component of a composite endpoint) will be set to treatment failure.
- *Early withdrawals.* Only visits following the early withdrawal visit will be set to treatment failure.
- *Rescue treatments.* Subjects who rescue with corticosteroids (before Day 45) or biologics will be set to treatment failure at all subsequent visits and continuous endpoints set to missing.
- *Missing baseline value.* For efficacy endpoints, a missing value at baseline will not be imputed, and the endpoint will be set to missing for all visits.

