4.4 Sample Size and Power

The sample size was calculated based on the mean difference in the cross-sectional area of the FSO by CT at Day 30 between the treatment and control sides from subjects in the PROGRESS study who underwent bilateral frontal BSD followed by unilateral placement of PROPEL Contour with the following assumptions:

- Expected mean difference of 9 mm² between the treatment and control sides
- A standard deviation (SD) of 18 mm² for side-to-side difference
- Target power of 95%
- Type I error rate of $\alpha = 0.05$, 2-sided

Internal, unpublished data suggest that SD = 18 is a reasonable assumption and that an achievable difference in mean cross-sectional areas of the FSO may be greater than 9 mm². The 9 mm² is deemed to be a clinically important difference to detect. Based on standard formulas for a t-test, a sample size of 56 subjects provides at least 95% power to detect a difference of 9 mm² in mean FSO cross-sectional area between treatment side and control side. Assuming up to 20% of subjects

with non-evaluable data on one or both sides, as it was reported in PROGRESS study report (R 28020), an additional 24 subjects will be enrolled for a total of 80 randomized subjects. Sample size calculations were carried out in PASS 14 (PASS 2015).

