4.5 Analysis Populations

The analysis of the primary and key secondary endpoints at Day 45 will be conducted on the intent-to-treat (ITT) population. The secondary endpoint analyses will be performed on the ITT and per-treatment evaluable (PTE) populations through Day 180. The exploratory endpoint analysis will be performed on the PTE population. The safety will be evaluated on the safety population. All analysis populations are defined below:

- *ITT Population.* All randomized subjects and sinuses in whom SBD followed by placement of PROPEL Contour in the target sinus was attempted. An attempt occurs when the physician introduces the delivery system into the subject's nostril with the intent of implant placement. Subjects' sinuses are analyzed in the treatment group to which they are randomized. This is the main analysis population for the primary and key secondary efficacy endpoints.
- *PTE Population.* All randomized subjects who have received PROPEL Contour in the target sinus, who have no major procedural protocol deviations (e.g., underwent study-related prior to informed consent, received treatment other than assigned by randomization), and for whom follow-up data are available. This population will be used for the secondary and exploratory endpoints.
- *Safety Population.* All subjects and sinuses exposed to PROPEL Contour. This population will be used for all summaries of AEs. Any subjects enrolled in the study who are not exposed to PROPEL Contour will be summarized separately.

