All statistical tests will be two-sided and interpreted at a 5% significance level. A p-value < 0.05 will be considered statistically significant. Unless stated otherwise, a two-sided 95% CI will be calculated and presented.

All available data at each time point will be presented. No imputations for missing data are planned, unless indicated otherwise.

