9.3.4 Sensitivity Analyses

Sensitivity analysis for medical or surgical intervention

Because intervention with oral steroids or surgical intervention may confound the primary efficacy endpoint, the following method will be applied to the analyses in cases where such interventions are performed:

- If a subject initiates oral steroids or undergoes revision ESS for CRS conditions attributable to the FSO/frontal recess before Day 45, this represents treatment failure. If the intervention occurs on the treatment side or both sides, the FSO cross-sectional area of the treatment side will be imputed with the value of the control side (i.e., side-to-side difference in FSO area is

zero). If the intervention occurs on the control side only, the FSO cross-sectional area in the control side will be imputed as zero (i.e., totally occluded).

- If a patient initiates oral steroids for other reasons not involving the FSO/frontal recess before Day 45, this does not represent treatment failure. In this scenario, the side-to-side difference in FSO cross-sectional area for that subject will be imputed as zero.
- No other data imputation rules will be applied in the planned statistical analyses.

Sensitivity analysis for missing data

Subjects with a missed visit, lost to follow-up, or with FSO cross-sectional area ‘unable to view’ by the independent, blinded reviewer will be considered as missing data. If more than 10% of the primary efficacy data are missing, the following imputation analyses will be performed to test the robustness of the primary efficacy conclusion in order:

- *Worst-case imputation.* The worst case of side-to-side difference in FSO area is zero. If the primary efficacy endpoint passes (p -value < 0.05) using worst-case imputation, then there is no need to do a best-case imputation analysis.
- *Best-case imputation.* The best case of side-to-side difference in FSO area is equal to the average for the treatment site.

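### SAP 6.7 sets steroid and biologic users' Day 45 areas to missing, 9.3.1 does not, and no planned analysis clearly keeps every measured ITT area

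*SAP*

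**What the plan says.** SAP 4.5 says: "The analysis of the primary and key secondary endpoints at Day 45 will be conducted on the intent-to-treat (ITT) population". SAP 9.3.1 defines the primary quantity as the Day 45 treatment-minus-control area averaged over the ITT subjects. The only reason it gives for a missing area is that the ostium could not be seen or measured.

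SAP 6.7 adds another reason: "Continuous efficacy endpoints will be set to missing for subjects who received any of the following not allowed medication post-baseline procedure". The list covers oral, parenteral, irrigated, breath-powered and nebulized corticosteroids and drug-eluting stents through Day 45, and biologics for CRS. The rescue item later in 6.7 repeats the instruction. The rule for binary endpoints asks whether use was for disease at the frontal ostium or recess; the rule for continuous endpoints does not. SAP 6.1 classes FSO area as continuous.

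SAP 9.3.4 has two sensitivity analyses.
- **Intervention.** It covers oral steroids and revision ESS only. For frontal disease, the difference becomes zero if the treated side or both sides are involved; the control area becomes zero if only the control side is. For an oral course given for another reason, which it says is not treatment failure, "the side-to-side difference in FSO cross-sectional area for that subject will be imputed as zero". It closes by ruling out any further imputation in the planned analyses.
- **Missing data.** It runs only if more than 10% of the primary data are missing. Its list begins "Subjects with a missed visit, lost to follow-up, or with FSO cross-sectional area" and ends with areas the core lab could not view.

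**The concern.** Under Protocol 15.1, a barred steroid before Day 45 may follow persistent or worse frontal inflammation together with a symptom-driven request. Under Protocol 19.3, subjects and treating investigators know which side has the implant. Steroid use can therefore depend on both outcome and assignment. Removing users conditions the primary comparison on an event after randomisation that may be linked to the quantity being measured.

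That could be tolerable if a planned analysis showed how much the result depends on it. None clearly does. Users of injected, irrigated, breath-powered or nebulized steroids, stents or biologics have no rule in the 9.3.4 intervention analysis and are not named in its missing-data list. A subject with an unrelated oral course and two readable sides is removed under 6.7 and given a zero difference under 9.3.4.

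**Working it through.** **The texts side by side, for a steroid user with both sides measured at Day 45**
- 9.3.1 and 9.3.3: the measured difference enters the t-test.
- 6.7: the value is missing.
- 9.3.4, intervention: a substituted value for oral steroids or revision ESS; no rule for other routes or biologics.
- 9.3.4, missing data: the worst case is zero and the best case is an average, so the measured value does not return.
- 9.1: observed-case leaves it missing. LOCF cannot fill it, because baseline is not carried forward and Appendix A has no CT between screening and Day 45.
- Table 1: no PTE run of the primary.

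**The plan's own figure.** SAP 4.4 gives: "Expected mean difference of 9 mm² between the treatment and control sides"; "A standard deviation (SD) of 18 mm² for side-to-side difference"; 95% power; two-sided 0.05. The effect size is 9/18 = 0.5. The paired t-test (noncentral t) needs 54 subjects for 95.0% power, and 56 give 95.7%, so the stated 56 is confirmed as at least 95%.

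**Effect on power.** If 20% of the 80 are not evaluable, 80 × 0.8 = 64 are measured. Then 64 − 56 = 8 (12.5%) can be deleted before n falls below 56. The main issue is bias rather than numbers.

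**Effect on the estimate.** Assumptions: the two sides are bivariate normal, the true difference is 9, the SD of the difference is 18, the side correlation ρ is 0.3–0.7, and the lowest 10% are deleted.
- Side SD: σ = 18/√(2(1 − ρ)) = 15.2 at ρ = 0.3 and 23.2 at ρ = 0.7.
- Cutting the lowest 10% of one side raises its mean by φ(1.2816)/0.9 × σ = 0.1755/0.9 × σ = 0.195σ. The other side rises by ρ times that.
- Shift in the difference: 0.195σ(1 − ρ) = 0.195 × 15.2 × 0.7 = 2.08, or 0.195 × 23.2 × 0.3 = 1.36.
- Treated side: 9 + 1.36 to 9 + 2.08 = 10.4 to 11.1. Control side: 9 − 2.08 to 9 − 1.36 = 6.9 to 7.6. Worse side, by simulation: 7.8 to 8.3.

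**Effect under no true difference.** With 80 × 0.9 = 72 left and treated-side deletion at ρ = 0.3, the SD after deletion is about 17.1. The noncentrality is 2.08/17.1 × √72 = 1.03 against a critical value of 1.99, which gives about 17%. At ρ = 0.7 it is about 9.5%.

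| Deletion follows | Estimate (true 9) | Favourable false positives (true 0, n = 72) |
|---|---|---|
| Worse side | 7.8–8.3 | 2.5% |
| Treated side | 10.4–11.1 | 9.5–17% |
| Control side | 6.9–7.6 | below 0.6% |

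With 58 left (64 less 6), the treated-side rate is 8–15%.

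**Why the 9.3.4 substitution does not fill the gap.** A zero control area turns the difference into the whole treated-side area. With no true effect, an assumed 5% risk of a single-side intervention on each side and a mean area of 30 mm², the mean shifts by about 0.05 × 30 = 1.5 mm² in favour of treatment.

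**What the as-measured analysis would cost in power.** Suppose a share p of the 64 are users averaging zero difference. The mean is 9(1 − p) and the SD is √(18² + p(1 − p) × 81).
- p = 10%: mean 8.1, SD 18.2, power 93.9%. Deletion leaves 58, power 96.3%.
- p = 20%: mean 7.2, SD 18.4, power 87.1%. Deletion leaves 51, power 93.8%.
- If users also average 9, as-measured power is 97.6% and deletion causes no bias.

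**The case against.** The strongest answer is that the primary t-test may already use areas as measured. SAP 9.3.1 is the specific section, its only reason for missingness is an unreadable ostium, and 9.3.4 excludes other imputation rules. The stated purpose of 9.3.4 is that intervention could confound the primary, which makes most sense if those subjects are still in it. This stands far enough that a reader should not infer that the as-measured comparison is certainly absent. It does not settle the matter: 6.7 states its rule twice, 6.1 brings FSO area within it, and SAP 10.2, writing about the primary and key secondary endpoints, cites 6.7 as the prespecified handling of missing data.

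Four other inferences go too far.
- That 9.3.4 overwrites every barred-steroid user: it covers oral steroids and revision ESS only.
- That values deleted under 6.7 cannot count toward the 10% trigger: this is a likely reading of the list, but 6.7 refers missing data to 9.1 and 9.3.4, and the list is not said to be exhaustive.
- That false positives are generally inflated: this happens only when deletion follows the treated side. Protocol 15.1 names no side, which fits worse-side deletion better. The 9.5–17% also assumes perfect selection on measured area. If the tendency to rescue correlates only 0.3–0.5 with that area, the shift scales by that factor and the rate is about 4–7%.
- That an ITT promise obliges a treatment-policy primary: ITT fixes who is analysed and in which group. The sponsor gives a reason, confounding, for handling steroid use separately.

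**Conclusion.** The concern holds as an unresolved conflict over the primary test, together with a missing analysis. Read literally, 6.7 removes measured areas that 9.3.1 keeps, and nothing says which prevails. Whichever does, no analysis is clearly identified as keeping all measured ITT areas.

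The size depends on which side drives steroid use, so the direction of bias is not known in advance. At 10% deletion it runs from about 2.1 mm² too low to 2.1 mm² too high on a true 9 mm². The figures rest on the SAP's 9 and 18 and on assumed values for the deletion share, side correlation, normality and selection. If users do not differ from other subjects in side difference, there is no bias. The point should be settled before the Day 45 data are unblinded.

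**What to change.** - In SAP 9.3.3, state whether 6.7 governs the primary t-test, and bring 9.3.1, 6.7 and the closing sentence of the 9.3.4 intervention analysis into line.
- In 9.3.4, prespecify the same t-test on all measured Day 45 side differences in ITT, regardless of steroid or biologic use, labelled as a sensitivity analysis.
- In the intervention analysis, keep the measured difference when the steroid was for a reason outside the frontal ostium or recess.
- Use one list of triggering interventions in 6.7 and 9.3.4, and say that values set to missing under 6.7 count toward the 10% trigger.

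The cost is SAP wording and one more run of a planned test on data already collected. The drawback is possible dilution, with the power loss shown above if users have no side difference. For that reason the analysis is added beside the primary and need not replace it.

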## 14 PRIOR AND CONCOMITANT MEDICATIONS

The following medication is allowed *prior* to and *post*-baseline procedure:

- INCS sprays prior to and post, starting after 7 days
- Orally inhaled steroids for control of asthma; and

- Stable regimens of leukotriene inhibitors and/or immunotherapy for allergies

The following medication is not allowed *prior* to the baseline procedure:

- A 30-day restriction for use of parenteral and injected steroids (e.g., Kenalog)
- A 14-day restriction for use of oral steroids, budesonide and/or any other sinus steroid irrigations/rinses or drops, nebulized steroids administered nasally; and
- A 45-day restriction for biologics for CRS treatment (such as Dupixent).

The following medication is allowed *post*-baseline procedure:

- Daily use of saline sprays/rinses/irrigations in both sinuses from Day 1
- Antibiotics if infection is suspected at any time during the study; and
- INCS sprays (excluding Xhance) in one or both sinuses starting after 7 days as clinically necessary.

The following medication not allowed *post*-baseline procedure:

- Other corticosteroids (e.g., oral, parenteral, injections, budesonide or other sinus steroid irrigations/rinses or drops, breath powered Xhance, nebulized steroids administered nasally or other drug eluting stents) through Day 45, unless clinically necessary, to ensure unbiased assessment of the primary endpoint; and
- Biologics for CRS treatment (e.g., Dupixent).

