6 STATISTICAL METHODS

6.1 General Considerations for Data Analysis

All analyses described in this plan are considered a priori analyses in that they have been defined prior to locking the database and reviewing unblinded results. All other analyses, if any, designed subsequent to locking the database will be considered post-hoc analyses and will be considered exploratory. Any post hoc analyses will be clearly identified in the clinical study report.

Continuous data such as cross-sectional area of FSO, FSO minimum diameter, FSOT volume, inflammation score, CRS side-specific symptom score, SNOT-22 score, and RSI score will be summarized in terms of the mean, standard deviation (SD), median, minimum, maximum, and number of observations, unless otherwise stated.

Categorical data such as Lund-Mackay score, Zinreich's modified Lund-Mackay score, adhesion/scarring grade, polypoid edema grade, and polyp grade will be analyzed quantitatively and summarized in terms of the mean, standard deviation (SD), median, minimum, maximum, and number of observations, unless otherwise stated.

Categorical data such as need for post-operative intervention in the frontal recess/FSO, patient satisfaction, implant delivery success rate, and economic measures will be summarized in terms of the number of subjects providing data at the relevant time point, frequency counts and percentages. If not stated otherwise, percentages will be presented with one decimal place. Percentages will not be presented for zero counts. Percentages will be calculated using n as the denominator. 100% will be presented without decimal places. Frequency distributions showing

findings by treatment side will be presented with counts, percentages and, where appropriate, exact 95% CI using the Clopper and Pearson method.

P-values greater than or equal to 0.001, in general, will be presented to 3 decimal places. P-values less than 0.001 will be presented as “< 0.001”.

95% Confidence intervals (CI) will be presented to 1 more decimal place than the raw data. Unless stated otherwise, a two-sided 95% confidence level will be calculated when confidence interval is presented.

Data from the protocol-specified visits (i.e., as reported in the case report form, CRF) will be used in the summary tables and data listings.

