6.6 Missing Dates

In analysis of AEs and medication, a complete date will be established in order to identify AEs or medication as occurring during treatment or not. For handling partially reported onset/start and outcome/end dates for AEs or medication the following algorithms are applied:

- AEs:
 - Missing onset day, but month and year present:
 - If baseline visit occurred in the same month and year as the occurrence of the AE, then the onset day of the event is assigned to the date of baseline visit.
 - Otherwise, the onset day is set to the first day of the month (e.g., XX-Sep-2021 is considered as 01-Sep-2021).
 - Missing onset day and month, but year present:
 - If baseline visit occurred in the same year as the occurrence of the AE, then the onset date of the event is assigned to the date of baseline visit.
 - Otherwise, the onset day and month is set to 01 January (e.g., XX-XXX-2021 is considered as 01-Jan-2021).

- Missing outcome day, but month and year present:
 - The day is set to the last day of the month (e.g., XX-Sep-2021 is considered as 30-Sep-2021).
- Missing outcome day and month, but year present:
 - The outcome day and month is set to 31 December (e.g., XX-XXX-2021 is considered as 31-Dec-2021).
- Medications:
 - Missing start day, but month and year present:
 - If baseline visit occurred in the same month and year as the occurrence of the medication, then the start day of the medication is assigned to the date of baseline visit.
 - Otherwise, the start day is set to the first day of the month (e.g., XX-Sep-2021 is considered as 01-Sep-2021).
 - Missing start day and month, but year present:
 - If baseline visit occurred in the same month in the same year as the occurrence of the medication, then the start date of the medication is assigned to the date of baseline visit.
 - Otherwise, the start day and month is set to 01 January (e.g., XX-XXX-2021 is considered as 01-Jan-2021).
 - Missing stop day, but month and year present:
 - The day is set to the last day of the month (e.g., XX-Sep-2021 is considered as 30-Sep-2021).
 - Missing stop day and month, but year present:
 - The stop day and month is set to 31 December (e.g., XX-XXX-2021 is considered as 31-Dec-2021).

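### SAP 6.7 removes continuous endpoint values for prohibited drug use without asking whether they were measured before the drug, and its two steroid windows differ

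*SAP*

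**What the plan says.** - **General rule, SAP 6.7.** "Continuous efficacy endpoints will be set to missing for subjects who received any of the following not allowed medication post-baseline procedure". There are two triggers. One is a list of corticosteroids ending "nebulized steroids administered nasally or other drug eluting stents) through Day 45". The other is "Biologics for CRS treatment (e.g., Dupixent"), which has no end day; Protocol 14 bars CRS biologics after the procedure, also without an end day. The sentence names no visit and does not compare drug and measurement dates.
- **Rescue treatments bullet, SAP 6.7.** This covers steroid rescue ("before Day 45) or biologics will be set to treatment failure at all subsequent visits and continuous endpoints set to missing".
- **Early withdrawals bullet, SAP 6.7.** "Only visits following the early withdrawal visit will be set to treatment failure".
- **What is continuous, SAP 6.1.** "Continuous data such as cross-sectional area of FSO, FSO minimum diameter, FSOT volume, inflammation score, CRS side-specific symptom score" and others.
- **Purpose of the steroid limit, Protocol 14.** Steroids other than nasal sprays are barred "through Day 45, unless clinically necessary, to ensure unbiased assessment of the primary endpoint".
- **Visit window, Protocol 7 and SAP Appendix A.** The Day 45 visit may fall 7 days either side, so the CT may fall on Days 38 to 52.

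**The concern.** The limit exists to keep drug-affected values out of the comparison. A CT taken before the drug is not affected by it, so deleting that CT does not serve the purpose. It also makes membership of the ITT primary analysis depend on something that happened after the measurement, and that may be related to how the sinuses looked at Day 45.

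The situation can arise in practice. SAP 5.2 runs the primary analysis after the last randomized subject's Day 45 assessments, and Protocol 5 plans nine months of enrolment. Early subjects will by then have medication records well past Day 45. Under the literal rule, whether a Day 45 area counts could depend on how long the subject has been followed.

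The two steroid windows and the unclear scope of the Rescue bullet add a second problem: two programmers following the same text can build different datasets for the primary test.

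**Working it through.** **1. Timing cases.** Study day is counted from the procedure (SAP 6.2.1), and Day 45 is read here as the study day.

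| Case | CT | First drug use | General sentence | Rescue bullet, if forward-only | Value relative to drug |
|---|---|---|---|---|---|
| A. Biologic | Day 45 | Day 100 | removed | kept | 100 - 45 = 55 days before |
| B. Steroid | Day 38 | Days 39-45 | removed | kept | 1 to 7 days before |
| C. Steroid | Day 52 | Days 46-51 | kept | kept | 1 to 6 days after |
| D. Steroid | Day 45 | Day 45, after the scan | removed | not triggered | before |
| E. Steroid | Day 45 | Day 30 | removed | removed | 15 days after |

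The readings agree on case E, the ordinary one. They disagree on A, B and D, where the general sentence removes a pre-drug value. Neither removes the post-drug value in C.

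**2. Tests reached.** There are six Day 45 tests: the primary and five key secondary (SAP 9.4.1). Area, area change, FSOT volume and minimum diameter rest on quantities that SAP 6.1 lists as continuous, so 4 of 6. The Zinreich score is listed there as categorical data analysed quantitatively, and need for intervention is binary.

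**3. The plan's sample size.** Inputs from SAP 4.4: difference 9 mm², SD 18 mm², two-sided alpha 0.05, target power 95%. Power is P(|T| > t(0.975, n-1)), with T noncentral t on n-1 degrees of freedom and noncentrality (9/18)√n. At n = 56 power is 95.69%, which reproduces the plan's figure of at least 95%. The smallest n that reaches 95% is 54 (95.02%); n = 53 gives 94.65%.

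**4. Power cost.** Taking the SAP's 20% non-evaluable, 80 × 0.80 = 64 pairs. The documents give no rescue or biologic rate, so the deletions below are assumptions.

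| Further pairs deleted | n | Power |
|---|---|---|
| 0 | 64 | 97.6% |
| 2 | 62 | 97.2% |
| 4 | 60 | 96.8% |
| 8 | 56 | 95.7% |
| 10 | 54 | 95.0% |

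Power falls below 95% only when more than ten further pairs are lost.

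**5. Shift in the mean.** Deleting one value x from 64 with mean 9 gives (64×9 - x)/63, a shift of (9 - x)/63. For a value one SD below the mean (x = -9) the shift is 18/63 = +0.29 mm². For one SD above (x = 27) it is -0.29 mm².

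As an illustration of systematic selection, assume a share r is removed and that drug use correlates 0.3 in size with the Day 45 difference, all normal. The shift is ±18 × 0.3 × φ(z)/(1 - r), where z is the normal quantile for r:
- r = 2%: 5.4 × 0.0484/0.98 = 0.27 mm²
- r = 5%: 5.4 × 0.103/0.95 = 0.59 mm²
- r = 10%: 5.4 × 0.1755/0.90 = 1.05 mm²

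At 5% the retained mean would be about 9.6 or 8.4 mm². Neither r nor the correlation, nor its sign, is given in the documents.

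**The case against.** **The forward-only reading is natural.** The bullets in SAP 6.7 are introduced as additional detail, so the Rescue bullet can be taken to limit the general sentence to later visits, which also fits the protocol's purpose. This is plausible. But the limit to later visits is attached to treatment failure, and no visit phrase follows the continuous-endpoint clause. The general sentence has no limit at all, so the two then conflict. The Early withdrawals bullet shows how plainly a forward limit can be stated. The forward-only reading also leaves case C untouched.

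**Day 45 may mean the visit, not the study day.** That would settle cases B and C. SAP 6.7 does not say so, the two lines would still differ for a drug taken on the visit date, and biologics are unaffected.

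**Endpoint-specific text may override 6.7.** SAP 9.3.1 sets the area to missing only when it cannot be viewed or measured, and 9.3.4 says no other imputation rules apply. This stands in part: that 6.7 reaches the primary test is a reading of its words. But 6.7 makes no exception for the primary endpoint, and the 9.3.4 sentence sits inside one sensitivity analysis. Nothing in 9.1 or 9.3.4 restores a removed measurement; the intervention analysis substitutes a zero difference or a zero control area.

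**Case A needs a protocol deviation and later data.** Biologics are barred throughout follow-up, and the documents do not say whether medication records after Day 45 feed the Day 45 analysis. This stands as a reason to expect few cases.

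**A stronger reading to avoid.** A reader might infer that the partial-date rule in SAP 6.6, which moves a start with a missing day to the first of the month, widens the problem by dating later drugs before the CT. The stated purpose of 6.6 is to classify medication as during treatment or not, and the SAP does not link it to 6.7. It forms no part of this point.

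**Conclusion.** The concern holds in limited form. As written, SAP 6.7 can delete Day 45 values obtained before any prohibited drug, can keep one obtained after a steroid when the CT is late in its window, and states two steroid windows that differ. It can reach the primary test and three of the five key secondary tests.

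This rests on a literal reading of the general sentence, on Day 45 meaning the study day for cases B and C, and, for biologics, on later medication records being used. Few subjects are likely to be affected, and the power loss is small.

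A reader might infer that the primary result is biased towards the implant, or that the trial is underpowered. The documents support neither: they give no rate and no direction of selection, and power stays at 95% after ten further deletions from 64 pairs. Severity is minor to should-fix: a wording correction to a rule that decides who is analysed.

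**What to change.** Before unblinding, amend the SAP:

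- **(a)** In 6.7, use one steroid window in both the general rule and the Rescue bullet, ending at the actual Day 45 CT or assessment.
- **(b)** State that a continuous value is set to missing only if the prohibited drug was first taken before the assessment that supplies the value, and that values obtained before first use are kept.
- **(c)** Leave the binary treatment-failure rule applying to subsequent visits.
- **(d)** In both intervention bullets of 9.3.4, replace 'before Day 45' with 'before the Day 45 CT'.
- **(e)** Where the dates do not establish whether drug or assessment came first, query the site. If the order stays unresolved, treat the drug as started before the assessment, so that a possibly affected value is not kept.

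The cost is SAP wording and occasional site queries. The protocol's medication rules do not change and no new assessments are needed: concomitant medication is already recorded at every visit, and CT dates are held.
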